4.0 Study Endpoints

The primary endpoint will be the determination of feasibility. Methods for establishing feasibility vary and include levels of acceptability, satisfaction, or usefulness. Drawing on similar published criteria, the intervention will be deemed feasible if the average score across all items is ≥ 3 on closed-ended survey items for adolescents, providers, and OOPs (Table 1).

Secondary endpoints will include the following:

- The completion of a referral for any contraceptive care as assessed through EMR review or follow-up phone calls.
- The initiation of contraception as assessed through EMR review or follow-up phone calls.
- Saturation of themes from qualitative interviews that have been coded and analyzed.

Hypotheses 1.1 and 1.2: To establish feasibility, we assess multiple constructs via survey items among all stakeholders (Table 1).

Hypotheses 1.2: We will determine referral completion and date for contraception initiation (Time 0) via participant contact and review of study/medical records at thirty days after the index visit.

Table 1: Mixed-Methodology Feasibility Assessment with Adolescent and Personnel Stakeholders

Construct	Source	Index Visit: Post-intervention	Time from Index Visit	Time from Initiation (Time 0)		
			30 Days*	3 mos*	6 mos*	
Acceptability - How do stakeholders react to the intervention?	Adolescent	S	S	S	S	
	Providers	S			SSI	
	Other personnel				S, SSI	
Demand - To what extent is the innovation likely to be used?	Providers				S, SSI	
	Other personnel				S, SSI	

SHORT TITLE: Reducing Pregnancy in the ED

	Study/Medical Record*				SMRR
Implementation - To what extent can the intervention be implemented as planned (including intervention fidelity)?	Providers	S			SSI
	Other personnel				S, SSI
	Study/Medical Record*	SMRR	SMRR		
Practicality - What factors make intervention delivery challenging or facilitate delivery?	Providers	S			S, SSI
	Other personnel				S, SSI
	Study/Medical Record*				SMRR
Adaptation – How does model perform in new setting?	Providers				SSI
	Study/Medical Record*				SMRR
Integration - To what extent can model be integrated within the system?	Providers				S, SSI
	Other personnel				S, SSI
Expansion - To what extent can model be expanded to provide service?	Providers				S, SSI
	Other personnel				S, SSI
	Study/Medical Record*				SMRR
Limited efficacy testing - What are rates of contraception initiation/continuation and referral completion?	Adolescent		S	S	S
	Study/Medical Record*	SMRR			SMRR

Legend: S=Survey, SSI= Semi-Structured Interview, SMRR= Study/Medical Record Review *+=/- 10 days

*Additional assessments include proportion enrolled, drug interaction or contraindications, intervention fidelity and duration, length of stay (participants vs. non-participants), rates of contraception initiation/continuation/referral completion, cost estimates

Data Sources: Sources include: surveys (via Research Electronic Data Capture – REDCap), semi-structured interviews, medical records, and study records (i.e., recruitment logs, interview transcripts, Providers/investigator field notes) (Table 1)

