2.0 Objectives

Evaluate intervention feasibility constructs: acceptability, demand implementation, practicality, adaptation, integration, expansion, and limited-efficacy. We will conduct a small randomized trial to assess feasibility and use mixed-methodology to explore contextual factors at the patient, provider, and system levels. In evaluating limited-efficacy, we compare two arms (MLI vs. eSOC) to determine size of effect rates on contraception initiation.

Hypothesis 1.1: The intervention will be deemed feasible by stakeholders: adolescents and organizational personnel (i.e., study providers, adolescent medicine specialists, hospital nursing and administrative leaders).

Hypothesis 1.2: Adolescents in the MLI arm will have greater contraception initiation rates relative to the eSOC arm at 30 days after the index ED visit.

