Prior to adolescent patients being enrolled, providers will be enrolled to participate in the study. Providers will be trained on motivational interviewing practices, contraception methods, as well as medication ordering practices.

Research team staff will screen potential study candidates via electronic tracking board. The research team will approach patients to ensure that they meet qualifications for the study. If qualifications are meet, the research team will provide consent/assent to the patient, conduct a pre-counseling survey, then notify a study provider of study status. Once the subject has been enrolled, the study provider will provide contraception counseling, while incorporating motivational interviewing techniques. Counseling sessions will be audio recorded and analyzed periodically for fidelity. At the completion of counseling, the study provider will offer the participant various contraception options and incorporate warm-referral practices to encourage follow-up at a local health clinic. The subject and provider will complete the Adolescent Post-Counseling Survey via REDCap at the end of their initial enrollment .

Immediately after the initial enrollment and at thirty-days post intervention, the research team staff will conduct a medical chart review. At thirty days, three months and six months post-intervention, a follow-up survey will be sent to the participant. OOP and provider staff will participate in semi-structured interviews that can be completed either in-person, virtually, or via telephone at 6-months to evaluate the feasibility of the study.

6.2

To help ensure the safety and validity of this study, we will ensure that provider staff are properly trained prior to enrollment. Training sessions will cover interviewing techniques, contraception, and ordering practices.

Members of the study team will also review audio recordings periodically for intervention fidelity.

6.3

Prior to approaching an adolescent participant, research team members will view the medical chart to ensure eligibility. Team members will look for the following, date of birth, custody status, and current contraception usage. In the post-intervention medical chart review, team members will look to see if a follow-up visit had been completed, and if so, if any services were obtained.

Surveys from adolescent participants will assess attitudes towards contraception, pregnancy prevention methods, perceived risk of contraception, and barriers to follow-up care.

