## Statistical analysis plan

We used R software (R Foundation for Statistical Computing) for analyses. In keeping with guidance discouraging the use of “statistical significance” and binary hypothesis testing based on arbitrary cutoffs (e.g.,  $P < .05$ ), we examined effect sizes along with  $P$  values and include  $P$  values without describing them as “significant” or “not significant.” Consistent with this approach, we did not attempt to control the familywise error rate (probability of at least one type I error across the study), which is not defined outside of binary hypothesis testing. We summarized closed-ended feasibility outcomes using descriptive statistics. We used an intention-to-treat analysis to assess preliminary efficacy and Fisher exact tests to compare arms on the percent of participants using contraception at 30 days. Dropouts during the index visit were treated as having no subsequent contraceptive use. Differences in average change score (e.g., attitudes) between arms were tested using nonparametric permutation tests.

*Primary Outcome:* We hypothesized the intervention would be deemed feasible by stakeholders. Drawing on similar examples in the literature, we determined a priori that the intervention would be feasible if the mean score across five Likert-scale survey items was  $\geq 4$  (range 1-5).

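### The primary feasibility rule is stated in two ways: a mean of at least 3 over all closed-ended items (Protocol 4.0), or at least 4 over five items (SAP)

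*Protocol*

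**What the plan says.** Protocol 4.0 states that "The primary endpoint will be the determination of feasibility" and gives the decision rule: "the intervention will be deemed feasible if the average score across all items is ≥ 3 on closed-ended survey items". The rule covers adolescents, providers and other organizational personnel and points to Table 1. The Protocol text gives neither the response scale nor the number of items.

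The SAP, under Primary Outcome, says "We hypothesized the intervention would be deemed feasible by stakeholders" and then "we determined a priori that the intervention would be feasible if the mean score across five Likert-scale survey items was" at least 4, on a range of 1 to 5. It does not name the five items or say which groups answer them.

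The rule decides Hypothesis 1.1 in Protocol 2.0: "The intervention will be deemed feasible by stakeholders: adolescents and organizational personnel".

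On timing, Protocol 6.0 says "The subject and provider will complete the Adolescent Post-Counseling Survey via REDCap at the end of their initial enrollment" and "At thirty days, three months and six months post-intervention, a follow-up survey will be sent to the participant". Table 1 likewise shows adolescent acceptability surveys at four points: index visit, 30 days, 3 months and 6 months.

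**The concern.** As written, the two rules differ in both the cut-off (3 against 4) and the item set (every closed-ended item against five). The Protocol sentence is current body text, not an amendment log. Nor is it the counselling-fidelity threshold, which also uses 3 but is a separate measure in Protocol 6.0.

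This is the only pass/fail criterion for the primary endpoint. If the documents can return opposite verdicts on the same data, the primary conclusion depends on which one is opened. The SAP also describes its rule as set a priori, while the Protocol sets out a different rule prospectively. The text does not show which came first, so that description is unsupported, though not disproved.

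Both rules are also incomplete. Neither picks a time point from the four adolescent surveys, and neither says whether the stakeholder groups are pooled or must each pass.

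**Working it through.** There is no derived figure to reproduce, because both cut-offs are stated rather than calculated. The check compares the rules and asks when they disagree.

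**Inputs**

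| | Protocol 4.0 | SAP, Primary Outcome |
|---|---|---|
| Cut-off | ≥ 3 | ≥ 4 |
| Items | all closed-ended | five, unnamed |
| Scale | not given | 1-5 |
| Respondents | three groups named | stakeholders, not listed |
| Time point | not given | not given |

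**1. Same items, different possible Protocol scales.** A Protocol score of 3 on a scale from lo to hi converts to 1-5 units as 1 + 4 × (3 − lo)/(hi − lo).

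| Assumed Protocol scale | Cut-off of 3 in 1-5 units |
|---|---|
| 1-5 | 1 + 4 × 2/4 = 3.00 |
| 0-4 | 1 + 4 × 3/4 = 4.00 |
| 1-4 | 1 + 4 × 2/3 = 3.67 |
| 0-5 | 1 + 4 × 3/5 = 3.40 |
| 1-7 | 1 + 4 × 2/6 = 2.33 |

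On 1-5, the rules disagree for any mean from 3.00 to just under 4.00. That is one of the four points of scale range (25% of the range, not a 25% chance of conflict). Of the scales tried, only 0-4 makes the cut-offs coincide, and neither document mentions it.

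Sampling error does not blur this much. Take a true mean of 3.5, an assumed SD of 1.0 and n = 30. The standard error is 1/√30 = 0.183, so each cut-off lies 0.5/0.183 = 2.74 standard errors away. The chance of meeting ≥ 3 is 0.997 and of meeting ≥ 4 is 0.003.

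**2. Different item sets.** Suppose the SAP's five items, with mean M, sit inside a Protocol set of k items, and the other k − 5 items average m. The overall mean is (5M + (k − 5)m)/k. It falls below a cut-off c when m < (ck − 5M)/(k − 5). The values of k and M are assumed, since the documents give neither.

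(a) Both on 1-5, c = 3, M = 4.00, so the SAP rule just passes. The Protocol rule fails only if m is below:
- k = 7: (21 − 20)/2 = 0.50, impossible on 1-5 (k = 6 likewise)
- k = 8: (24 − 20)/3 = 1.33
- k = 10: (30 − 20)/5 = 2.00
- k = 15: (45 − 20)/10 = 2.50
- k = 20: (60 − 20)/15 = 2.67

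(b) Protocol coded 0-4, so c = 4 in 1-5 units, and M = 4.20. The SAP rule passes and the Protocol rule fails if m is below:
- k = 6: (24 − 21)/1 = 3.00
- k = 10: (40 − 21)/5 = 3.80
- k = 20: (80 − 21)/15 = 3.93

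So with more than five items, equal cut-offs alone would not make the rules agree.

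**3. Could all items mean the same five?** Table 1 marks surveys for six constructs (acceptability, demand, implementation, practicality, integration, expansion) for providers, and for the same six for other personnel. Five items could cover six constructs only if an item served more than one.

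**The case against.** The strongest reply is that the wording differs but the substance has not been shown to. The Protocol gives no scale and no item count. If its items were coded 0-4 and there were exactly five of them, the two rules would be identical. Nothing in the text strictly excludes that. It needs both conditions together, however. Neither is documented, and the six surveyed constructs make the second hard to accept. Even then, the two statements would still need reconciling for a reader.

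Three further points stand in part:

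- **Direction.** On a common 1-5 scale, the SAP passing while the Protocol fails is remote. Case (a) puts the five-item mean exactly at the boundary. At a mean of 4.5 with k = 10, the other items would have to average below (30 − 22.5)/5 = 1.50. The material case is the band from 3.00 to just under 4.00, where the SAP is the stricter rule.
- **Timing.** The survey instruments and some front pages are not in the text available, so a missing date is not itself a fault, and no change of rule is alleged. The a priori wording calls for confirmation from a dated record.
- **Weight.** Feasibility outcomes are summarised descriptively, and no sample size or procedure in the available text depends on the cut-off. That limits the knock-on effects, but this is still the primary endpoint.

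**Conclusion.** The concern holds. The only pass/fail threshold for the primary endpoint is stated in two current texts that differ in cut-off and in described item set, and the texts do not say which governs. That is a contradiction in the decision rule, not merely missing detail, and it must be fixed.

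The contradiction in wording rests on no assumption. Its numerical size does: the one-point band of conflicting verdicts requires the same items and a 1-5 Protocol scale. The band is narrower for 1-4 or 0-5, wider for 1-7, and vanishes for 0-4. Conflicts in the other direction depend on an assumed item count above five. Nothing here suggests that the bar was lowered or that a change was concealed.

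**What to change.** Reconcile the two passages into one primary rule, stated identically for both documents, that fixes:

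- the cut-off and the response scale;
- the items, by name;
- the survey time point that counts;
- whether stakeholder groups are pooled or judged separately.

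Add a dated note saying which rule was in force at first enrolment and why the other differs. The SAP is written in the past tense. If analysis is already done, a dated clarification attached to both documents would serve better than rewriting the Protocol after the fact. Keep the a priori wording only if a dated record shows the rule was set before enrolment; if such a record exists, citing it settles the timing question.

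Report the feasibility verdict under both rules, the Protocol's on its own items and scale and the SAP's on its five.

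The cost is one definition, one note and a few table rows, with no new data. The downside is that the feasibility conclusion may be shown to depend on the rule used.

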5.0 Study Intervention/Investigational Agent

- 5.1 The study intervention is the implementation of Emergency Department-based contraceptive counseling. A provider will provide this confidential, comprehensive, 10-15-minute counseling. The counseling will assess patients' preferences regarding different methods, knowledge about methods, personal motivations, and environmental factors that may influence contraceptive use, such as partner preference. After counseling is complete, enrolled subjects that have been randomized into the MLI group will have the opportunity to accept birth control and a referral for follow-up care.

For Emergency Contraception

Plan B (also called levonorgestrel) is taken by mouth by a woman to prevent pregnancy after she has already had unprotected sex. It is available over-the-counter for any person to buy. Plan B has no serious or lasting side-effects and leaves the body within a few days. Some women (fewer than one in five) have mild and short-term side-effects, including irregular bleeding from the vagina, belly pain, being tired, nausea (feeling like you might throw up).

SHORT TITLE: Reducing Pregnancy in the ED

For hormonal contraception

Many formulations of hormonal contraception exist including those with estrogen and progesterone combined (e.g., Sprintec, Ortho-Evra, Yaz). The most common side effects from combination hormonal contraception are mild and include: irregular vaginal bleeding, breast tenderness, nausea, and mood changes. Serious adverse events may occur. Older women who smoke are at increased risk of myocardial infarction or stroke. There is no increased risk of myocardial infarction or stroke among healthy nonsmoking women who use the pill. Blood clots in the legs and elsewhere are slightly more frequent with contraceptive use, but the risk is very low, and lower than the increased risk of clotting that occurs with pregnancy. There is no increased risk of birth defects in babies born to women who have taken hormonal contraception while pregnant, but a woman should not use hormonal contraception if she is pregnant.

Medroxyprogesterone acetate: The most common side effects from DMPA are mild and include: irregular menstrual cycles, cessation of menstrual periods, headache, and weight gain. Serious adverse events may occur. Use of DMPA may cause loss of bone mineral density, which may lead to an increased risk of developing osteoporosis. The decrease in bone calcium is most concerning if the patient has bone disease, family history of osteoporosis, or anorexia nervosa. Older women who smoke are at increased risk of myocardial infarction or stroke. There is no increased risk of myocardial infarction or stroke among healthy nonsmoking women who use the pill. Blood clots in the legs and elsewhere are slightly more frequent with contraceptives, but the risk is very low, and lower than the increased risk of clotting that occurs with pregnancy. There is no increased risk of birth defects in babies born to women who have taken hormonal contraception while pregnant, but a woman should not use hormonal contraception if she is pregnant.

Ortho Evra and Xulane (Norelgestromin/ethynodiol) is birth control patch that works by stopping ovulation. It may also change cervical mucus to prevent the sperm from reaching the egg and change the lining of the uterus to prevent a fertilized egg from implanting in the uterus. Side effects can include: breast tenderness or enlargement; headache; menstrual cramps; mild fluid retention or weight gain; mild skin irritation at the application site; nausea; stomach pain, cramps, or bloating; vaginal spotting or breakthrough bleeding; vomiting.

NuvaRing (ethynodiol and etonogestrel) is a birth control vaginal ring that contains female hormones that stop ovulation (the release of an egg from an ovary). This medicine also causes changes in the cervical mucus and uterine lining, making it harder for sperm to reach the uterus and harder for a fertilized egg to attach to the uterus. Side effects may include: headache; vaginal irritation or discharge, cervical pain; menstrual cramps; mood changes, decreased sex drive; nausea, vomiting, stomach pain; breast pain or tenderness; acne; or weight gain.

SHORT TITLE: Reducing Pregnancy in the ED

The most common side effects from subdermal implants include changes in menstrual bleeding patterns; headaches; vaginitis; weight gain; acne; breast pain; viral infection such as sore throats or flu-like symptoms; stomach pain; painful periods; mood swings, nervousness, or depressed mood; back pain; nausea; dizziness; pain and pain at the site of insertion.

For Non-Hormonal Contraception

Common side effects for non-hormonal contraception (Copper IUD, Phexxi) include irritation, dryness and/or allergic reactions.

Risk of emotional distress: Participants may experience increased stress over the sensitive survey questions. However, we feel this risk is minimal and we have included information in the consent process that reminds participants that they are not required to answer questions that make them feel uncomfortable. In the emergency department, there are always advocates available for patients and families, if needed, including health care providers, social workers, and patient advocates. In this study setting, if a participant expresses a concern or need that is outside of the scope of this project (e.g., sexual assault), we will refer those participants back to their ED treating team, as is our standard practice. During the consent process, we will inform participants that most of the information they share during the study will be kept confidential except in rare cases where their safety is at risk or mandated reporting is in effect

- 5.2 To decrease risk of serious adverse events, we will follow regulations and recommendations in accordance with the Food and Drug Administration. We will prescribe the dosage regimen which contains the least amount of estrogen and progesterone that is compatible with a low failure rate and the needs of the individual patient. We will screen participants for predisposing conditions and duration of previous DMPA use. Women with these conditions should not use hormonal contraceptives: women with stroke or blood clot, circulation problems (especially if caused by diabetes), a hormone-related cancer such as breast or uterine cancer, abnormal vaginal bleeding, liver disease or liver cancer, severe high blood pressure, migraine headaches, or a heart valve disorder. Further, DMPA should not be used as a long-term method (i.e., longer than 2 years) unless other methods are considered inadequate.
- 5.3 Participants will be advised of all potential adverse events and instructed to seek care if symptoms develop or they have concern about such an event. In the case of illness or injury resulting from this study, treatment is available at CM or CHOP, and can be provided at the usual charge. Participants may also see care at the hospital-affiliated Title X Clinic, which provides reproductive care at reduced cost.

6.0 Procedures Involved

We propose a randomized trial of our contraceptive counseling intervention (MLI vs. eSOC) with mixed methods feasibility evaluation at patient, provider, and system levels. Feasibility constructs are: acceptability, demand, implementation, practicality, adaptation, integration, expansion, and limited-efficacy.

Using an electronic board that tracks patient data in real time, the research study staff will identify and enroll adolescent participants (N=98) before they meet with a provider. Due to possible COVID precautions, research staff will have the capability of recruiting patients remotely. Consenting and the study visit will take place on the same day of enrollment during the patients ED visit. If necessary, a member of the research team may call into the patient room via Microsoft Teams or CMH office phones to contact the patient up to five times. Follow up surveys at thirty-days, three months, and six months are administered via REDCap and may be sent through Twilio or e-mail. Members of the research team may also call participants up to five times to administer the surveys verbally using either Microsoft Teams or CMH phones.

We will use a care model demonstrated as best practice in clinic-based settings³⁶ and train providers using adapted materials publicly available (e.g., slide decks, written materials).³⁷⁻⁴⁰ Adaptations are needed for vulnerable adolescent populations that are mindful of coercion and will include use of brief Motivational Interviewing (MI) strategies to facilitate autonomy and focus on patient preference. MI training for providers will focus on these skills: open questions, reflective listening, and pulling for change talk.⁴¹⁻⁴⁵ Providers will receive nine hours of training (e.g., prescribing, adolescent-centered counseling, technology) and demonstrate competency (mean fidelity score ≥ 3 , appendix 1) prior to continued recruitment.

As adolescents mature along different trajectories, we plan open-ended questions to ask about intention, experiences (self/referents), and contraceptive qualities. Given that many in our ED reported relationship abuse, we will use a trauma-informed approach (i.e., realize, recognize, respond, resist re-traumatization) to foster collaboration, explore safety, and offer harm reduction strategies.⁴⁸⁻⁴⁹ We will help participants 1) map information onto values and lifestyle, and 2) anticipate and solve problems, including identification of a trusted adult. We will address risk misperceptions use visual aids, and counsel dual protection with condoms. Based on our work and others, providers will provide 10-15 minutes for counseling; this is easily integrated into most ED visits. Counseling sessions will occur after patients have completed triaging, without interrupting the evaluation of standard of care services.

Providers will also have access to educational material, which can be distributed to adolescents randomized in MLI arm. These documents include the following: FDA Approved factsheets (Ring, Pill, Patch, Mini Pill, Progestin IUD, Implant, Non-Hormonal Gel, Emergency Contraception, and Depo), Switching Birth

SHORT TITLE: Reducing Pregnancy in the ED

Control, IUD Facts, Implant Facts, Contraception Choices, and CMH Clinic Hours and Locations. The contraception handouts that are being provided will help to provide further clarifications regarding medication effectiveness, adherence instructions, as well as medication side effects.

C6eii. Adolescent Randomization and Treatment: Randomization will be in a 1:1 ratio. Due to potential influence of previous contraception use on uptake, we will use block randomization with randomly selected blocks of 4 or 8 to balance allocation of those with previous use equally between arms.⁴⁸ [name] will create the master randomization list for both Children's Mercy and Children's Hospital of Philadelphia, placing each assignment in a sealed envelope numbered sequentially from 001.⁵⁴ Participant IDs will be assigned beginning with 001. After consent, a research assistant will open the corresponding envelope to carry out the arm assignment, notifying the providers before counseling is completed.

All participants receive contraceptive counseling. Per evidence-based guidelines,⁵²⁻⁵³ MLI participants can receive contraception (one injection, three-month supply of pill/patch/ring, or subdermal implant) in the ED, or prescription for another method if desired. If a patient in this group desires another method that is not being covered by the study, patient will be made aware of their responsibility to cover the cost of the medication either out of pocket, or by using their own insurance. Due to credentialing and staffing constraints, intrauterine devices will only be available at referral clinics. MLI participants who want to initiate contraception must complete a urine pregnancy test, which must be negative. MLI participants who initiate contraception will be given a take home pregnancy test that is to be completed two weeks after enrollment. eSOC participants will have the opportunity of being referred to a follow-up appointment to discuss and begin contraception. Subjects in this group will not begin contraception in the Emergency Department or given a prescription. All participants will be referred to an adolescent gynecologist, hospital-affiliated adolescent clinic, or Title X clinic for additional care and to initiate or follow-up on contraception.

MLI participants will have a “warm transfer” to follow-up on or initiate, if preferred, selected method. Warm transfers occur with the assistance of a provider scheduling the follow-up appointment. Doing this in such a way should help to minimize barriers with navigating the healthcare system. The provider will share detailed clinic information including hours of operation and contact the receiving site. We will assist with scheduling (sending multiple reminders) and transportation. eSOC participants will be given printed information on clinics.

C6eiii. Intervention Fidelity: Counseling sessions will be audio-recorded and reviewed periodically to ensure for fidelity to content and use of MI strategies using a tool adapted from our previous work and the CHOICE Project, a clinic-based intervention efficacious for increasing contraception uptake in family-planning clinics.⁵⁴⁻⁵⁵ We will provide feedback to individual APPs if mean fidelity score ≤ 3 .

SHORT TITLE: Reducing Pregnancy in the ED

Prior to adolescent patients being enrolled, providers will be enrolled to participate in the study. Providers will be trained on motivational interviewing practices, contraception methods, as well as medication ordering practices.

Research team staff will screen potential study candidates via electronic tracking board. The research team will approach patients to ensure that they meet qualifications for the study. If qualifications are meet, the research team will provide consent/assent to the patient, conduct a pre-counseling survey, then notify a study provider of study status. Once the subject has been enrolled, the study provider will provide contraception counseling, while incorporating motivational interviewing techniques. Counseling sessions will be audio recorded and analyzed periodically for fidelity. At the completion of counseling, the study provider will offer the participant various contraception options and incorporate warm-referral practices to encourage follow-up at a local health clinic. The subject and provider will complete the Adolescent Post-Counseling Survey via REDCap at the end of their initial enrollment .

Immediately after the initial enrollment and at thirty-days post intervention, the research team staff will conduct a medical chart review. At thirty days, three months and six months post-intervention, a follow-up survey will be sent to the participant. OOP and provider staff will participate in semi-structured interviews that can be completed either in-person, virtually, or via telephone at 6-months to evaluate the feasibility of the study.

6.2

To help ensure the safety and validity of this study, we will ensure that provider staff are properly trained prior to enrollment. Training sessions will cover interviewing techniques, contraception, and ordering practices.

Members of the study team will also review audio recordings periodically for intervention fidelity.

6.3

Prior to approaching an adolescent participant, research team members will view the medical chart to ensure eligibility. Team members will look for the following, date of birth, custody status, and current contraception usage. In the post-intervention medical chart review, team members will look to see if a follow-up visit had been completed, and if so, if any services were obtained.

Surveys from adolescent participants will assess attitudes towards contraception, pregnancy prevention methods, perceived risk of contraception, and barriers to follow-up care.

6.4

SHORT TITLE: Reducing Pregnancy in the ED

Enrolled adolescents will receive follow-up surveys at 30-days, 3-months, and 6-months after their initial enrollment at their ED visit. The questions asked will assess subjects' attitudes towards contraception methods, access to care, and contraception efficacy. Enrolled patients may complete the survey over the phone with a member of the research team. A link may also be sent via text messaging using Twilio or other approved messaging system or to their email address.

